Official title: Efficacy of kinect-based versus tablet-based cognitive training through simulations of instrumental activities of daily living: a pilot study with psychiatric patients

Unique protocol ID: I/2021

Document date: 20 October 2021

DELIBERATION CE/CSCP No. 1/2021, of JANUARY 19th

Deliberation on the request for ethical approval of the research project entitled "Efficacy of kinect-based versus tablet based cognitive training through simulations of instrumental activities of daily living: a pilot study with chronic psychiatric patients" submitted to the Ethics Committee of Casa de Saúde Câmara Pestana (CSCP).

A – REPORT

A.1 The CSCP's Ethics Committee and the Clinical Board, responsible for coordinating clinical investigation processes in CSCP, analyzed the request for ethical approval of a study submitted by [name]. She is currently performing a professional internship in psychology and proposed a research project entitled "Efficacy of kinect-based versus tablet-based cognitive training through simulations of instrumental activities of daily living: a pilot study with chronic psychiatric patients." For this purpose, the models 187, 189, and 218 were carefully analyzed. The study's main goal is to contribute to the stimulation and maintenance of cognitive functioning through a combined intervention (cognitive training + physical activity/kinect-based intervention) or an individual intervention (cognitive training/tablet-based intervention).

A.2 To formalize our decision, we analyzed the following documents that were submitted by the researcher, [name]: a) study protocol, b) response to the request to conduct the study, c) statement of commitment, d) research project, and e) informed consent.

A.3 This study consists of a randomized controlled longitudinal trial that aims to: a) identify which type of intervention is more suited to patients with chronic psychiatric disorders, i.e., the combined intervention or the individual intervention; and b) to evaluate the impact of both interventions in the long-term (3 months follow-up) in several domains (e.g., cognitive functioning, quality of life, mood, and functional capacity).

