Cognitive deficits are a nuclear feature of several psychiatric disorders, leading to decreased functional abilities and quality of life. Besides facilitating the inclusion of more ecologically valid stimuli and training tasks, technology-based cognitive training methods allow more dynamic interactions with the cognitive training content, which can enhance patients' motivation and engagement in the therapeutic process. The modality of interaction with the cognitive training content may influence patients' response to cognitive training interventions. For instance, cognitive training through the tablet essentially requires hand movements (e.g., interaction with the training tasks by touching the correct stimuli). In contrast, cognitive training through the Kinect – a more natural user interface – involves performing broad range movements (e.g., interaction with the training tasks by making specific "body" movements to select the correct stimuli). Literature shows that natural user interfaces provide a training experience closer to reality. As a result, we hypothesize that cognitive training using natural user interfaces can lead to more significant gains in cognitive and non-cognitive domains and, possibly, enhance transfer for daily life outcomes.

Objectives

This study aims to analyze which cognitive training experimental condition – Tablet versus Kinect – results in greater cognitive, mood, quality of life, and functional gains in a sample of chronic psychiatric patients.

Methods

Trial Design

Single-blind pilot randomized controlled trial.

Inclusion criteria

- Chronic Psychiatric diagnosis;
- Maximum age: 75 years old;
- Being able to read and write;
- Relatively preserved language abilities (expressive and receptive language);
- Preserved visual and auditory acuity;
- Having no motor limitations;
- Having no medical history of neurological conditions (e.g., stroke, traumatic brain injury, multiple sclerosis, etc.)

Exclusion criteria

- Experiencing an acute psychiatric episode.

Procedure

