Eligible patients will be randomly allocated to both training conditions – kinect and tablet-based cognitive training. Then, a certified psychologist will collect patients' sociodemographic and clinical data and perform a baseline neuropsychological assessment. The 14-session cognitive training program inspired by instrumental activities of daily living will be applied to all patients. Sessions will be around 30 minutes and will be administered 2 times per week. The computerized cognitive training application used will be Musiquence, which was initially developed for cognitive stimulation purposes within the context of dementia syndromes. Both groups will perform the

same cognitive training program; the only thing that will differ will be the setup (kinect versus tablet).

Neuropsychological assessment

A comprehensive neuropsychological assessment will be delivered to all patients in three different moments, namely:

- Pre-intervention: baseline assessment, immediately before the beginning of the intervention;
- Post-intervention: immediately after the intervention;
- Follow-up: 3-months after the intervention.

The neuropsychological assessment protocol encompasses a set of primary and secondary outcome measures that will be briefly described below:

Primary outcome measures

- Global cognitive functioning: Montreal Cognitive Assessment (MoCA) (Freitas et al., 2013);
- Processing speed: Symbol Search and Digital Symbol Coding from Wechsler Adult Intelligence Scale – Third Edition (WAIS-III; Wechsler, 1997; 2008);
- Attention: Toulouse-Piéron Cancellation Test (TP) (Toulouse & Piéron, 1986);
- Verbal memory: Free and Cued Selective Reminding Test (FCSRT) (Lemos et al., 2015);
- Visual memory and visuospatial abilities: Rey Complex Figure Test (RCFT) (Rey, 1998);
- Executive functions: Frontal Assessment Battery (FAB) (Lima et al., 2008), Semantic and Phonemic Verbal Fluency Tests (Cavaco et al., 2013);

Secondary outcome measures

- Depressive symptoms: Beck Depression Inventory II (BDI-II) (Beck et al., 1996);
- Quality of life: World Health Organization Quality of Life – Bref (WHOQOL-Bref) (Quality of life) (Canavarro et al., 2006);
- Functional abilities: Adults and Older Adults Functional Assessment Inventory (IAFAI) (Sousa et al., 2013).

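### Does the 3-month aim in A.3(b) commit the trial to a per-arm efficacy question that its two-arm design cannot answer?

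*Protocol*

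**What the plan says.** The Protocol speaks to the aims in two places, written by different parties.

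The first is the ethics committee's deliberation. Section A.3 summarises the study as a randomised, controlled, longitudinal trial with two aims. Aim (a) is to "identify which type of intervention is more suited to patients with chronic psychiatric disorders", the combined or the individual one. Aim (b) is "to evaluate the impact of both interventions in the long-term (3 months follow-up) in several domains". Aim (a) carries no time point; aim (b) names no comparator.

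The second is the investigators' own text. The background states the hypothesis: "we hypothesize that cognitive training using natural user interfaces can lead to more significant gains in cognitive and non-cognitive domains". The Objectives then ask which of the two conditions, tablet or Kinect, "results in greater cognitive, mood, quality of life, and functional gains in a sample of chronic psychiatric patients". Both statements are comparative, and neither names a time point.

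The Procedure describes two arms only: "Eligible patients will be randomly allocated to both training conditions". It adds: "The 14-session cognitive training program inspired by instrumental activities of daily living will be applied to all patients". The arms differ only in the setup through which the programme is delivered. The section on neuropsychological assessment supplies the timing: "A comprehensive neuropsychological assessment will be delivered to all patients in three different moments", namely before the intervention, immediately after it and 3 months after it. The primary and secondary outcome measures are listed under that schedule.

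**The concern.** Aim (a) already covers the comparison, so aim (b) can be taken as something additional: the lasting effect of each training by itself. The committee's statement of the main goal in A.1, which speaks of stimulating and maintaining cognitive functioning by one intervention or the other, points the same way.

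On that reading the design falls short. With no untrained group, the only reference for an arm is its own baseline. Change from baseline mixes any training effect with retest gain over three assessments, natural course and usual care. If both arms improved or held steady at 3 months, a reader could conclude that each training works or preserves function, with no randomised comparison behind that conclusion. An SAP could not supply the missing comparator. Because the Objectives name no time point, A.3(b) is also the only place that states a purpose for the 3-month assessment, so the worry deserves a check.

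**Working it through.** The Protocol gives no sample size, effect size or SD, so there is no figure of its own to reproduce. The check has two parts.

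**What each reading can identify.** Write the mean change in an arm as t + s, where t is the arm's own training effect and s the change that would have occurred without training. Take s as equal in the two arms, which randomisation supports in expectation. The Protocol gives no value for s; a range of -0.2 to +0.5 SD is assumed.

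- Per arm: own effect = observed change - s. For an observed gain of 0.4 SD:
  - s = -0.2: 0.4 - (-0.2) = 0.6
  - s = 0: 0.4 - 0 = 0.4
  - s = 0.2: 0.4 - 0.2 = 0.2
  - s = 0.5: 0.4 - 0.5 = -0.1
- For an arm that holds steady (change 0), the own effect runs from 0 - (-0.2) = +0.2 to 0 - 0.5 = -0.5 SD. A larger sample does not narrow these ranges.
- Between arms: (tK + s) - (tT + s) = tK - tT, so s cancels. With tK = 0.3 and tT = 0, the Kinect arm's own change is 0.10, 0.30, 0.50 and 0.80 SD over the four values of s, while the difference is 0.30 SD at each.

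The algebra is right, but it holds for any trial of two active treatments. It shows what the design can and cannot answer; it does not show that this Protocol asks the unanswerable question.

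**Which question the Protocol asks.**

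1. *Authorship.* A.3(b) is the committee's summary of documents submitted to it (listed in A.2). The investigators' aim stands under Objectives.
2. *Contrast.* The Objectives ask which condition gives greater gains, and the hypothesis has the same form. Both target tK - tT, the quantity that is free of s. Neither claims efficacy for an arm by itself.
3. *Time point.* The assessment section measures all patients immediately after and 3 months after the intervention and lists the outcomes under that schedule. Objectives and schedule together give the Kinect-versus-tablet comparison at both moments. An Objectives paragraph that does not repeat the visit schedule is ordinary drafting.
4. *Consistency.* A.3(b) follows directly on the comparative aim (a), in a sentence that calls the study randomised and controlled. Reading it as that comparison carried to 3 months is natural and agrees with the Objectives. Even on the other reading, the two texts differ in scope and do not contradict each other.

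**The case for a change.** The best case for keeping the point is that it would cost almost nothing to settle. One could add to the Objectives that the 3-month evaluation is the Kinect-versus-tablet comparison and that within-arm changes are descriptive. Naming the question asked at a time point belongs in a protocol, and in a pilot the temptation to rely on within-arm change is real. Precision illustrates this. With assumed arm sizes and a baseline-to-follow-up correlation r of 0.7, the 95% half-width of the between-arm difference is t(0.975, 2n - 3) × sqrt(2(1 - r²)/n). That is 2.052 × sqrt(2 × 0.51/15) = 0.535 SD at 15 per arm, and about 0.37 SD at 30. A result showing no clear difference while both arms improve is quite possible.

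The caution about interpretation stands: within-arm gains in this trial would not show that either training works. It does not follow that the plan is wrong. The Objectives already state the identifiable contrast, and the schedule already provides the data for it. How within-arm change is presented is a reporting rule that an SAP can carry, and one may exist unseen. The half-widths rest on assumed arm sizes and correlations and measure the precision of a pilot; they have no bearing on whether the aims are stated wrongly. An added sentence would also leave the committee's wording in place and, if it named only the 3-month assessment, could suggest a priority over the immediate post-intervention one that the investigators have not stated.

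**Conclusion.** The concern does not hold. It is true that no untrained arm is described and that A.3(b), taken per arm, could not be answered. That reading is optional, however, and attaches to the committee's paraphrase. The investigators' Objectives and hypothesis are comparative, and the schedule covers the 3-month assessment for all patients. Carrying out the Protocol as written leads to the randomised Kinect-minus-tablet difference at 3 months.

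The effect on that contrast is nil: in the illustration it stays at 0.30 SD for every value of s, given that non-training change is equal in the two arms and follow-up is complete. The spread of 0.6 to -0.1 SD for a 0.4 SD within-arm gain depends on the assumed range for s and concerns a claim that the investigators' Objectives do not make. Spelling out the time point would be a wording preference, so no change to the Protocol is needed.

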Cognitive deficits are a nuclear feature of several psychiatric disorders, leading to decreased functional abilities and quality of life. Besides facilitating the inclusion of more ecologically valid stimuli and training tasks, technology-based cognitive training methods allow more dynamic interactions with the cognitive training content, which can enhance patients' motivation and engagement in the therapeutic process. The modality of interaction with the cognitive training content may influence patients' response to cognitive training interventions. For instance, cognitive training through the tablet essentially requires hand movements (e.g., interaction with the training tasks by touching the correct stimuli). In contrast, cognitive training through the Kinect – a more natural user interface – involves performing broad range movements (e.g., interaction with the training tasks by making specific "body" movements to select the correct stimuli). Literature shows that natural user interfaces provide a training experience closer to reality. As a result, we hypothesize that cognitive training using natural user interfaces can lead to more significant gains in cognitive and non-cognitive domains and, possibly, enhance transfer for daily life outcomes.

Objectives

This study aims to analyze which cognitive training experimental condition – Tablet versus Kinect – results in greater cognitive, mood, quality of life, and functional gains in a sample of chronic psychiatric patients.

Methods

Trial Design

Single-blind pilot randomized controlled trial.

Inclusion criteria

- Chronic Psychiatric diagnosis;
- Maximum age: 75 years old;
- Being able to read and write;
- Relatively preserved language abilities (expressive and receptive language);
- Preserved visual and auditory acuity;
- Having no motor limitations;
- Having no medical history of neurological conditions (e.g., stroke, traumatic brain injury, multiple sclerosis, etc.)

Exclusion criteria

- Experiencing an acute psychiatric episode.

Procedure

Eligible patients will be randomly allocated to both training conditions – kinect and tablet-based cognitive training. Then, a certified psychologist will collect patients' sociodemographic and clinical data and perform a baseline neuropsychological assessment. The 14-session cognitive training program inspired by instrumental activities of daily living will be applied to all patients. Sessions will be around 30 minutes and will be administered 2 times per week. The computerized cognitive training application used will be Musiquence, which was initially developed for cognitive stimulation purposes within the context of dementia syndromes. Both groups will perform the

same cognitive training program; the only thing that will differ will be the setup (kinect versus tablet).

Neuropsychological assessment

A comprehensive neuropsychological assessment will be delivered to all patients in three different moments, namely:

- Pre-intervention: baseline assessment, immediately before the beginning of the intervention;
- Post-intervention: immediately after the intervention;
- Follow-up: 3-months after the intervention.

The neuropsychological assessment protocol encompasses a set of primary and secondary outcome measures that will be briefly described below:

Primary outcome measures

- Global cognitive functioning: Montreal Cognitive Assessment (MoCA) (Freitas et al., 2013);
- Processing speed: Symbol Search and Digital Symbol Coding from Wechsler Adult Intelligence Scale – Third Edition (WAIS-III; Wechsler, 1997; 2008);
- Attention: Toulouse-Piéron Cancellation Test (TP) (Toulouse & Piéron, 1986);
- Verbal memory: Free and Cued Selective Reminding Test (FCSRT) (Lemos et al., 2015);
- Visual memory and visuospatial abilities: Rey Complex Figure Test (RCFT) (Rey, 1998);
- Executive functions: Frontal Assessment Battery (FAB) (Lima et al., 2008), Semantic and Phonemic Verbal Fluency Tests (Cavaco et al., 2013);

Secondary outcome measures

- Depressive symptoms: Beck Depression Inventory II (BDI-II) (Beck et al., 1996);
- Quality of life: World Health Organization Quality of Life – Bref (WHOQOL-Bref) (Quality of life) (Canavarro et al., 2006);
- Functional abilities: Adults and Older Adults Functional Assessment Inventory (IAFAI) (Sousa et al., 2013).

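### Is the single-blind label undone because patients see their device and are tested after allocation with no safeguard described?

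*Protocol*

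**What the plan says.** The whole statement on blinding is the line under Methods, Trial Design: "Single-blind pilot randomized controlled trial". The blinded party is not named.

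The background before the Objectives contrasts the two ways of working. Of one arm it says that "cognitive training through the tablet essentially requires hand movements"; the Kinect arm "involves performing broad range movements". The same paragraph expects larger gains from natural user interfaces. The Procedure adds that both groups follow one training program and that "the only thing that will differ will be the setup (kinect versus tablet").

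On the order of events, the Procedure reads: "Eligible patients will be randomly allocated to both training conditions – kinect and tablet-based cognitive training. Then, a certified psychologist will collect" sociodemographic and clinical data "and perform a baseline neuropsychological assessment". Under Neuropsychological assessment there are three assessments: before the intervention, immediately after it, and 3 months later. The tester at the second and third is not named, and neither is the person who runs the sessions.

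**The concern.** A reader who takes the label at face value will ask who is blind. It cannot be the patient with respect to the device, since one arm touches a screen and the other moves the whole body. Staff who run the sessions see the device too. That leaves the assessor. Yet the Procedure allocates first and tests second. It says nothing about withholding the allocation from the tester, separating testing from training, or asking patients not to mention their device.

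The stakes are real in principle. Several primary measures (MoCA, FAB, FCSRT, RCFT, verbal fluency) are administered or scored by an examiner. Both arms receive active training with the same content, so the difference of interest may be modest. The protocol also states which direction it expects. An examiner who knew the arm and shared that expectation could shift scores towards Kinect, and the shift would go straight into the between-arm difference. The depression and quality-of-life questionnaires are answered by patients who know their device.

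**Working it through.** The protocol gives no figure to reproduce on this point, so the check is mainly a reading of the text.

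1. **Can the patient be the blinded party?** Not for the device: the background and the Procedure make it the visible difference between arms. Patients could be unaware of the study hypothesis, but the protocol does not say so. The realistic reading is a blinded assessor.

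2. **Does the Procedure contradict a blinded assessor?** It gives a sequence (allocation, then the psychologist's baseline assessment) and no more. A sequence does not convey the allocation to the tester; an assessor who is not told the arm can test after randomisation. No sentence says that the psychologist holds or sees the allocation.

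3. **Does the text link the tester to the trainer?** No. The psychologist is named only for the sociodemographic and clinical data and the baseline assessment. The post-intervention and follow-up testers, who matter most for bias, are not identified, and nobody is named as delivering sessions. An examiner who has seen the arm at those two assessments is possible under the text but is not stated in it.

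4. **How large could the effect be?** The bias ratio is (shift from examiner expectation) / (true difference between arms), both in SD units. Neither quantity is in the protocol. Assume a shift of 0.1 to 0.3 SD and a true difference of 0.2 to 0.3 SD:

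| Shift (SD, assumed) | True difference (SD, assumed) | Ratio |
|---|---|---|
| 0.1 | 0.3 | 0.1/0.3 = 33% |
| 0.1 | 0.2 | 0.1/0.2 = 50% |
| 0.3 | 0.3 | 0.3/0.3 = 100% |
| 0.3 | 0.2 | 0.3/0.2 = 150% |

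The arithmetic is correct, but both ranges are assumed. With an assessor who is unaware of the arm, the numerator is zero and so is the ratio. The calculation also applies one shift to every primary test, although Symbol Search, the coding task and the Toulouse-Piéron test are timed or cancellation tasks that leave less to examiner judgement than scoring the RCFT or the FAB.

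5. **What would a change achieve?** Naming the assessor as the blinded party would write down what the label can realistically mean already. Marking the patient-answered questionnaires as open-label would change no result, because patients' knowledge of their device cannot be avoided in this comparison. Dividing testing and training between the intern researcher mentioned in the ethics deliberation (A.1) and the psychologist in the Procedure assumes that these are two people, both available. The protocol does not say so; if they are not, an extra assessor would be needed.

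**The case for a change.** The strongest case for a change is that blinding is a matter of design and conduct. It belongs in the protocol, and a later statistical analysis plan cannot make an assessor blind. The Trial Design and Procedure text is shown, so the gap is not a redaction. A reader who sees the label will assume a protection whose method is nowhere described, and allocating before baseline makes that protection harder to keep. A few sentences would settle it.

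Much of this stands. The blinded party is not named, no safeguard is described, the directional expectation is in the text, and the place for such detail is the protocol. It would be reasonable to ask the investigators who was blinded and how, and a report of the trial should say so.

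What does not stand is the step from silence to failure. To say that neither patient nor assessor is protected when the protocol is followed goes too far: as written, one party is blind and the method is left open. The ethics deliberation (A.2) also lists a research project and an informed consent among the papers submitted, so the division of roles may be described there. That is a weaker argument, since the protocol is where one would look first.

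**Conclusion.** No change to the plan follows. The label is incomplete, but no passage contradicts it, and the reading that makes sense of it, an assessor unaware of the arm, can be carried out under the Procedure as written. This is a gap in detail that a competent team fills sensibly.

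The conclusion rests on one assumption, that those who test and score are in fact kept unaware of the allocation. The protocol neither confirms nor denies this. If it were shown that the same person trained and tested patients, the label would be wrong and the examiner-scored outcomes would be open to bias. The protocol does not show that. No size can be attached to the point: the 33% to 150% range depends entirely on assumed inputs and falls to zero under a blinded assessor.

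### Random allocation is placed before the baseline assessment, with no statement that the arm is withheld until baseline is recorded: an avoidable risk to the reference point for all gains

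*Protocol*

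**What the plan says.** The protocol's Procedure section opens with allocation: "Eligible patients will be randomly allocated to both training conditions". The next sentence continues: "Then, a certified psychologist will collect patients' sociodemographic and clinical data and perform a baseline neuropsychological assessment". The Neuropsychological assessment section dates the first of the three assessments as "Pre-intervention: baseline assessment, immediately before the beginning of the intervention". The other two follow the end of training and come 3 months later.

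On masking, the Trial Design section says only "Single-blind pilot randomized controlled trial". It names no masked party.

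On the arms, the Procedure section says that the program is the same in both and that "the only thing that will differ will be the setup (kinect versus tablet"). The background explains the difference in use: "cognitive training through the tablet essentially requires hand movements", whereas the Kinect "involves performing broad range movements".

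The Objectives section asks which condition "results in greater cognitive, mood, quality of life, and functional gains in a sample of chronic psychiatric patients".

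**The concern.** The objective is a comparison of gains, so each outcome is measured against this one baseline. If patient or assessor knows the arm when baseline is taken, then effort, self-report or scoring could differ between arms before any training has been given. The background supplies a reason to take this seriously: it expects larger gains from natural interfaces such as the Kinect and links interaction with the content to motivation and engagement.

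Baseline is also special among the three assessments. Patients inevitably learn their set-up at the first training session, so at both later assessments they know it. Only at baseline can they still be unaware of it. Allocating first gives up that protection unless the arm is withheld, and the protocol gives no reason for the order. A baseline recorded with knowledge of the arm cannot be replaced afterwards by any choice of analysis. The order of allocation and assessment is trial conduct that the protocol itself fixes, not something a statistical analysis plan would settle.

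**Working it through.** The protocol gives no figure on this point, so the main check is a reading of the sections against each other.

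**1. Order.** The two sentences in Procedure are joined by a sequence word, so baseline follows allocation. The definition of the pre-intervention assessment ties baseline to the start of training, not to allocation. It is compatible with allocation coming earlier, so the sections do not contradict each other, but it does not put baseline first either.

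**2. Masking at baseline.** A single-blind design masks one party. The possibilities are:

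- Assessor masked: the patient may know the arm at baseline, unless it is withheld.
- Patient masked: the assessing psychologist may know it, unless it is withheld.
- Allocation made but disclosed to nobody until baseline is done: neither knows. This also fits the text, but the text does not require it.

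The blinding statement alone therefore does not protect both parties at baseline. Only non-disclosure, or a different order, would.

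**3. What an arm-dependent baseline would do.** Suppose there is no true difference between arms. Let b be the shift in one arm's mean baseline score in SD units, p the fraction of it still present at a later assessment, and r the slope of the later score on baseline. The slope equals the pre-post correlation if the SD is the same at both times, which is assumed here.

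- Bias in the difference in gains: p·b − b = −(1 − p)·b
- Bias in the baseline-adjusted difference: p·b − r·b = (p − r)·b

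The first is zero only if p = 1, the second only if p = r.

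None of b, p and r is in the protocol. For illustration only, take b = −0.2 SD and r from 0.5 to 0.85:

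| p | Gains: −(1 − p)·b | Adjusted, r = 0.5 | Adjusted, r = 0.85 |
|---|---|---|---|
| 0 | −1 × (−0.2) = 0.20 | −0.5 × (−0.2) = 0.10 | −0.85 × (−0.2) = 0.17 |
| 0.5 | −0.5 × (−0.2) = 0.10 | 0 × (−0.2) = 0 | −0.35 × (−0.2) = 0.07 |
| 1 | 0 | 0.5 × (−0.2) = −0.10 | 0.15 × (−0.2) = −0.03 |

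For b = −0.1 SD every entry halves: 0.10, 0.05 and 0 SD for gains, and 0.05 to 0.085, 0 to 0.035 and −0.05 to −0.015 SD for the adjusted difference. All signs reverse if the shift is upward. The table shows that neither analysis reliably removes such a shift. It does not show that a shift occurs.

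**The case against.** The strongest objection is that the protocol dates allocation, not disclosure. Nothing in it says that anyone is told the arm before baseline. A trial with masked assessors whose patients learn their set-up at the first session satisfies every sentence. This stands. A reader might infer that, whichever party is masked, the other must know the arm at baseline. The text does not support that; it leaves the possibility open and does no more.

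Second, the text at hand is short and some of it was removed. Report A.2 lists a research project and a consent form submitted alongside the study protocol, and a non-disclosure step could be described there. This too stands, and it is why the point rests on the stated order rather than on the unnamed masked party. The latter alone would be missing detail.

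Third, the larger figures in the table need p = 0, which is doubtful: whoever knows the arm at baseline will usually know it later, so persistence is at least as plausible, and full persistence cancels in the gains. This is right, and the figures should not be read as an estimate. It does not justify the order, because the cancellation depends on an equality that nobody can check.

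Fourth, both arms are active and receive the same program, which may weaken expectation effects, and the trial calls itself a pilot. Fair, and a reason to keep the point in proportion.

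Finally, a reader might add weight by counting the outcomes that share this baseline. The number of comparisons says nothing about whether any baseline score is shifted.

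**Conclusion.** The point holds as an avoidable open risk in a stated procedure. Allocation precedes baseline, the text available does not keep the arm from both patient and assessor until baseline is recorded, and gains are measured from that baseline.

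The size and direction of any bias cannot be estimated from the protocol. Under the assumed shifts of 0.1 to 0.2 SD, the bias in gains runs from nothing to 0.20 SD in absolute value. A 0.1 SD shift would be nearly harmless, and nothing in the document indicates that a larger one would occur. A reader might take the finding as evidence that the trial's baselines are biased; the documents do not support that. The case for a change is that the remedy is almost free, while a compromised baseline cannot be repaired in the analysis.

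**What to change.** In Procedure, reverse the two steps: collect the demographic and clinical information and complete the baseline battery first, then randomise and disclose the arm, with training starting straight after. Baseline then still falls directly before training, as the Neuropsychological assessment section requires.

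If the present order must stay, add a sentence requiring that the arm is not disclosed to patient or assessor until the baseline is recorded.

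As an accompanying clarification, name the masked party in the Trial Design section. Reordering protects only the baseline; what protection exists after training and at 3 months depends on who is masked.

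The cost is a reordering of two sentences, or one added sentence, plus a few words on masking. Tests, staff and timing relative to training are unchanged. The downsides are an occasional baseline battery for a patient who withdraws before allocation and, possibly, a notification to the ethics committee.
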